3.2 Rationale of study design

The study uses a randomized, patient and investigator-blinded, parallel-group design on top of standard-of-care, which has been used in other clinical trials investigating new treatments in patients with acute stroke due to ICH. Treatments are randomized, and blinded to patients and investigators to avoid potential reporting bias. Parallel groups are used because strokes are usually one-time events.

Perihematoma edema (PHE) has attracted significant attention as a mechanism of secondary injury after ICH, thereby contributing to both short-term morbidity and long-term disability ([Selim and Norton 2018](#)).

Commercially Confidential Information

The modified Rankin Scale (mRS) is a widely-used clinical instrument, and is considered the current standard assessment for stroke outcomes by most Health Authorities. The follow-up observation period of 90 days for assessing improvement in functional disability is a well-established time point for stroke studies, including trials in ICH ([CPMP Points to Consider 2001](#)). The 90-day mRS score has been used as an endpoint in many contemporary clinical stroke trials, including INTERACT2 ([Anderson et al 2013](#)), ATACH ([Qureshi et al 2010](#)), SAMURAI-ICH ([Koga et al 2014](#)), and ENOS ([The ENOS Trial Investigators 2015](#)).

Studies published by [Fu et al \(2014a, 2014b\)](#) with fingolimod showed reduction of PHE and potential clinical benefit in stroke treatment with an S1P receptor modulator. The pilot data published by [Fu et al \(2014a\)](#) with fingolimod need to be reproduced under more rigorous trial conditions in a larger population and in another geography. Despite this earlier study with fingolimod, the sponsor has selected BAF312 (siponimod) for further development, as the considerably shorter half-life of BAF312 may be advantageous in an acute setting, such as ICH.

3.3 Rationale for dose/regimen, route of administration and duration of treatment

Commercially Confidential Information

Dose titration is introduced with the aim to reduce the bradycardic effects of S1P₁ modulators during treatment initiation. The proposed i.v. dose-titration scheme is based on estimations of the HR effects of BAF312 and therapeutic need to achieve fast, effective concentrations in ICH patients. There is currently no knowledge to predict the duration of treatment necessary to reduce secondary brain damage due either to perihematomal edema (PHE) or to other potential mechanisms. The choice of i.v. administration in the Stroke Unit/NICU setting is based on the standard practice of maintaining acute stroke patients NPO on admission until the presence or absence of dysphagia can be determined.

3.4 Rationale for choice of comparator

Placebo is the only possible comparator given the absence of any approved treatment for acute stroke due to ICH.

3.5 Rationale for choice of background therapy

All patients in the study should receive supportive standard-of-care treatment for ICH, as laid down in the guidance publications of the American Heart Association and the American Stroke Association ([Hemphill et al 2015](#)), and the European Stroke Organisation ([Steiner et al 2014](#)).

3.6 Purpose and timing of interim analyses/design adaptations

Commercially Confidential Information

3.7 Risks and benefits

The risk to patients in this trial must be minimized by compliance with the eligibility criteria and study procedures, close clinical monitoring, and clear instructions to the Investigator on how to manage symptomatic bradycardia if it occurs.

Bradycardic effect – Treatment initiation with BAF312 results in transient decrease in HR in a dose-dependent manner, with nadir ~3-4 h after the first dose. In a clinical study in MS patients (CBAF312A2201) without dose titration, five cases of second degree AV blocks were reported: 3/29 in the 2 mg group and 2/50 in the 10 mg group. Implementation of dose titration effectively mitigated the occurrence of bradycardic events. In this study, the dose is titrated to the target daily dose of CCI BAF312. The need to achieve fast therapeutic concentration was carefully weighed against the need to prevent bradycardic effects. Unlike ischemic stroke, in which reflex tachycardia and increased blood pressure is typically allowed to persist (to some extent) to maximize perfusion of the ischemic penumbra, in hemorrhagic stroke most supportive therapies are aimed at lowering blood pressure to minimize likelihood of acute expansion of the initial hematoma. Given this, transient bradycardia carries significantly less risk in the ICH patient population than in patients with ischemic stroke.

During the first 48 hours of treatment, all patients will be on continuous CV telemetry in Stroke Units/Neurointensive Care Units, and special attention will be given to the monitoring of the HR. In case of symptomatic bradycardia, the Investigator should follow the guidance given in [Section 6.6](#). Under those predefined conditions, BAF312 treatment must be interrupted. When the heart rate has recovered, the treatment may be started again, as judged by the Investigator.

Risk of infection - The core PD effect of BAF312 is dose-dependent reduction of peripheral lymphocyte counts to 20-30 % of baseline due to their sequestration in the lymphoid tissues. As a consequence, there is an increased risk of infections. Patients with low baseline lymphocyte count are excluded from the study. There were no reports of increased bacterial infections between drug and placebo in the MS population with S1P₁ modulators (fingolimod

and BAF312). Although the risk of infection is considered small given the short treatment duration of 14 days, in this critically-ill population this risk might be higher.

Cases of progressive multifocal leukoencephalopathy (PML), have been reported with another S1PR modulator, fingolimod, but is extremely unlikely in this population due to the short treatment duration. Nevertheless, signs of CNS infections will be routinely monitored, promptly investigated, and treated as per standard medical practice. Although not the preferred imaging modality for PML *per se*, all study patients will have CT imaging of the brain performed at 7 and 14 days after ICH, as well as ongoing neurological examinations (see [Assessment schedule](#)). Effective diagnostic and therapeutic strategies should be employed in patients with infections.

Aspiration pneumonia – Respiratory tract infections were reported only in 3 patients with MS on BAF312 (N=235) and none on placebo (N=61). While the risk of aspiration pneumonia cannot be excluded in this population, it is not believed to be increased by BAF312 treatment. All ICH patients must be monitored in the Stroke Unit/NICU setting for at least the first 48 hours after ICH, and standard-of-care treatment interventions should be implemented in cases of aspiration pneumonia.

Urinary tract infections – In the clinical trials conducted in MS patients, the incidence of overall infections was not different between placebo and BAF312 (5% in BAF312 and 3.5% in placebo). Patients with ICH requiring urinary catheterization might be at a higher risk of urinary infections, which should be treated per the standard-of-care in the Stroke Unit/NICU.

Blood pressure – In the healthy volunteer and MS population, the blood pressure lowering effect of BAF312 was very weak upon initiation. Small elevations in blood pressure were seen with siponimod treatment. The mechanism of these effects is unclear, but is potentially the result of unopposed natural sphingosine-1-phosphate ligand stimulation of S1PR type 2/3 (S1P2/3) endothelial receptors, owing to the strong functional antagonism of S1P1 by siponimod ([Brinkmann et al 2010](#)). Even taking into account that the population for this study is likely to be older, minimal effects are nonetheless expected with this BAF312 dose and short treatment duration.

Elevated liver function tests – In the Phase 2 dose-finding study in MS patients, elevated liver function tests > 3 x ULN were noted in 4.3% of patients in BAF312 (10 mg and 2 mg) groups. However, the short treatment duration of this study will likely reduce the frequency of treatment-related liver enzyme elevations.

Macular edema – The occurrence of macular edema with BAF312 in the present study is unlikely given the short treatment duration. However, the Investigator should be aware that patients with diabetes mellitus and previous uveitis might be at risk of developing macular edema. If the patient reports vision disturbances, they should be referred to an ophthalmologist for OCT measurement.

Radiation dose considerations from CT scans – Patients enrolled in this trial will have CCI non-contrast head CT scans- two as part of routine standard-of-care for ICH determination and follow-up (one at presentation/inclusion and another 24-48 hours later- corresponding to V1 and V2 in the [Assessment schedule](#)) and CCI follow-up study scans CCI at Days CCI 14 (V10). Scans from CCI Day 14 will be used for quantitative assessment of efficacy of BAF312 via determination of hemorrhage and edema volumes, as described elsewhere in this document. The effective radiation dose per scan is expected to be

approximately 2 mSv, amounting to a total of 8 mSv including the two standard-of-care scans (V1 and V2) ([McCollough et al 2015](#) and [Smith-Bindman et al 2009](#)). This is considered to be a minor to intermediate risk level corresponding to the benefit to the patient (category IIb based on [ICRP 62 1992](#)) and is balanced against the possible substantial societal benefit gained from the trial ([European Commission Radiation Protection 1998](#) and [ICRP 62 1992](#)). The radiation dose from CT scans will be in accordance with local clinical practice and regulations.

The investigators must regularly review the degree of burden and the risk threshold for the patients enrolled in this study.

There may be unknown risks with BAF312 which may be serious and unforeseen in the ICH patient population.

The treatment with BAF312 may benefit ICH patients. In a pilot study with another S1P₁ modulator (fingolimod), treated patients showed a reduction of neurologic impairment compared to placebo, regained a Glasgow Coma Scale score of 15 by Day 7; and had a NIHSS score reduction of 7.5 vs 0.5 in the placebo group ([Fu et al 2014a](#)).

Taking into account the nature of the known risks, the short duration of treatment, and the lack of alternative specific therapies for ICH, it is considered that the overall risk-benefit is favorable to study the therapeutic effect of BAF321 in ICH patients.

3.7.1 Blood sample volumes

A maximum of 300 mL of blood is planned to be collected over a period of 3 months from each patient as part of the study. Additional samples may be required for safety monitoring.

Timings of blood sample collection are outlined in the [Assessment schedule](#) (Section 8.1).

A summary blood log is provided in the Site Operations Manual (SOM). Instructions for all sample collection, processing, storage and shipment information is also available in the SOM and Central Laboratory Manual.

See [Section 8.9](#) regarding the potential use of residual samples.

4 Population

The study population consists of adult patients with stroke due to ICH fulfilling the eligibility criteria listed below at screening.

Approximately 33 patients per treatment group (~65 patients in total) will be randomized to obtain at least 60 completed study subjects (Day 14).

4.1 Inclusion criteria

ICH patients eligible for inclusion in this study must fulfill **all** of the following criteria:

1. Male or female patients aged 18 to 85 years (inclusive).
2. Written informed consent obtained before any study assessment is performed.

If the patient is not able to give the informed consent personally, consent by a relative or legal representative is acceptable.

3. Spontaneous, supratentorial intracerebral hemorrhage in cerebral cortex or deep brain structures (putamen, thalamus, caudate, and associated deep white matter tracts) with a volume ≥ 10 mL but ≤ 60 mL (calculated by the ABC/2 method, after [Kothari et al 1996](#)) determined by routine clinical MRI or CT.
4. Patients with the onset of ICH witnessed and/or last seen healthy no longer than 24 hrs previously.
5. Patients with Glasgow Coma Scale (GCS) best motor score no less than 5 (brings hands above clavicle on stimulus to head or neck).

4.2 Exclusion criteria

ICH patients fulfilling **any** of the following criteria are **not** eligible for inclusion in this study:

1. Use of other investigational drugs within 5 half-lives of enrollment, or until the expected pharmacodynamic effect has returned to baseline (for biologics), whichever is longer.
2. History of hypersensitivity to any of the study drugs or to drugs of similar chemical classes (e.g., fingolimod).
3. Current use of concomitant medications with potent CYP2C9/3A4 inhibitory or induction potential.
4. *Intentionally blank – removed with protocol amendment #2.*
5. Infratentorial (midbrain, pons, medulla, or cerebellum) ICH.
6. Candidates for surgical hematoma evacuation or other urgent surgical intervention (i.e., surgical relief of increased intracranial pressure) on initial presentation. If during the treatment period surgical hematoma evacuation or surgical intervention to lower intracranial pressure becomes indicated, the investigational treatment should be stopped.
7. Patients with intraventricular hemorrhage (IVH) having a Graeb score (oGS) of >3 on initial presentation. Patients **must not** have blood in the 4th ventricle (0 points max), and may only have blood in the 3rd ventricle in the absence of ventricular expansion (≤ 1 point max). Trace or mild hemorrhage in either or both lateral ventricles (≤ 1 point each) is permitted. Patients with hydrocephalus determined radiographically on initial presentation are excluded regardless of oGS (see [Section 8.8](#)).
8. Secondary ICH due to:
 - aneurysm
 - brain tumor
 - arteriovenous malformation
 - thrombocytopenia, defined as platelet count of $<150,000/\mu\text{l}$
 - known history of coagulopathy
 - acute sepsis
 - traumatic brain injury (TBI)
 - disseminated intravascular coagulation (DIC)
9. Prior disability due to other disease compromising mRS evaluation, thereby interfering with the primary outcome, operationally defined as an estimated mRS score (by history) of ≥ 3 before ICH for patients ≤ 80 years of age. For ICH patients 81-85 years of age, estimated mRS by history prior to ICH **must** be ≤ 1 (no significant disability despite symptoms).

10. Preexisting unstable epilepsy.
11. Patients with active systemic bacterial, viral or fungal infections.
12. Concomitant drug-related exclusion criteria:
 - Intravenous immunoglobulin, immunosuppressive and/or chemotherapeutic medications.
 - Moderate immunosuppressives (e.g. azathioprine, methotrexate) and/or fingolimod within 2 months prior to randomization.
 - Stronger immunosuppressives (e.g. cyclophosphamide, immunosuppressive mAb) within (minimally) 6 months prior to randomization, or longer with long-lasting immunosuppressive medications as determined by the investigator.
13. Cardiovascular exclusion criteria:
 - Cardiac conduction or rhythm disorders including sinus arrest or sino-atrial block, heart rate <50 bpm, sick-sinus syndrome, Mobitz Type II second degree AV block or higher grade AV block, or preexisting atrial fibrillation (either by history or observed at screening).
 - PR interval >220 msec. Long QT syndrome or QTcF prolongation >450 msec in males or >470 msec in females on screening electrocardiogram (ECG).
 - Patients receiving treatment with QT-prolonging drugs having a long half-life (e.g., amiodarone).
14. Any of the following abnormal laboratory values prior to randomization:
 - White blood cell (WBC) count < 2,000/ μ l (< 2.0×10^9 /L)
 - Lymphocyte count < 800/ μ l (< 0.8×10^9 /L)
15. Pregnant or nursing (lactating) women, where pregnancy is defined as the state of a female after conception and until the termination of gestation, confirmed by a positive hCG laboratory test.
16. Patients with any other medically unstable condition or serious laboratory abnormality as determined by the investigator.

The Investigator must ensure that all patients being considered for the study meet the inclusion criteria, above.

Patient selection is to be established by checking through all eligibility criteria at screening. A relevant record (e.g. checklist) of the eligibility criteria must be stored with the source documentation at the study site.

Deviation from any entry criterion excludes a patient from enrollment into the study.

5 Restrictions for Study Subjects

For the duration of the study, patients should be informed and reminded of the restrictions outlined in this section.

5.1 Contraception requirements

Women of child bearing potential must be informed that taking BAF312 may involve unknown risks to the fetus if pregnancy were to occur during the study; and agree that in order to participate in the study they must use highly effective methods of contraception during study. Highly Effective contraception methods include:

- Total abstinence from heterosexual intercourse (when this is in line with the preferred and usual lifestyle of the patient). Periodic abstinence (e.g., calendar, ovulation, symptothermal, post-ovulation methods) and withdrawal are **NOT** acceptable methods of contraception.
- Female sterilization (have had surgical bilateral oophorectomy with or without hysterectomy) or tubal ligation at least six weeks before taking study treatment. In case of oophorectomy alone, only when the reproductive status of the woman has been confirmed by follow up hormone level assessment.
- Male sterilization (at least 6 months prior to screening). For female patients on the study, the vasectomized male partner should be the sole partner for that patient.
- Other forms of contraception that have comparable efficacy (failure rate <1%), for example placement of a non-hormonal intrauterine device (IUD) or intrauterine system (IUS).

Study CBAF312X2207 will enroll only ICH patients with basal ganglia (putamen, caudate, thalamus) primary hemorrhages. This population consists mainly of older patients with long histories of smoking, hypertension, and/or diabetes. The study specifically excludes patients with secondary ICH (i.e., due to malignancy, vascular malformation, aneurysm, trauma, etc.), which is more often the underlying cause in younger patients. As such, with these Inclusion/Exclusion Criteria, it is very unlikely that our study will enroll women of child-bearing potential. Furthermore, given the significant short-term disability of our ICH patients, it is highly unlikely that they will be sexually active during the treatment phase of our study, consisting of the first 14 days after their stroke; or immediately thereafter, when they will very likely be in an inpatient rehabilitation hospital.

In the unlikely event that a female ICH patient with child-bearing potential enrolled in our study chooses to become sexually active immediately after the treatment phase, but while still in the follow-up phase of the study, all female ICH patients of child-bearing potential should not use hormone-containing methods of systemic contraception, oral or injectable, for the duration of the study. Alternative methods of contraception should be discussed between these patients and their personal physicians, and be decided upon by the patient with the counsel of her doctor.

Contraception requirements start at the Screening/Baseline Visit, and are to be maintained until at least 30 days after the last administration of study drug.

If there is any question that the patient will not reliably comply, the patient should not be entered or continue in the study. Male patients must be informed that if a female partner becomes pregnant while he is enrolled in the study, contact with the female partner will be attempted to request her consent to collect pregnancy outcome information.

5.2 Prohibited treatment

Use of medications displayed in [Table 5-1](#) are **NOT** allowed during treatment with BAF312 due to increased risk of immunosuppression, confounding of efficacy and/or potential interaction with study treatment (**NB**: CYP2C9 and CYP3A4 are the major metabolizing enzymes for BAF312).

Table 5-1 Prohibited Medications

Medication	Action to be taken
Immunosuppressive/chemotherapeutic medications or procedures, including cyclosporine, azathioprine, methotrexate, and immunomodulatory mABs	Stop taking. If not possible, consider discontinuation of study treatment
Medication that suppress AV conduction (e.g. carbamazepine, non-dihydropyridine calcium-channel blockers, or cardiac glycosides) with the exception of beta-blockers	Stop taking. If not possible, consider discontinuation of study treatment
Strong inhibitors of CYP2C9 or CYP3A4 (Table 21-1)	Stop taking. If not possible, consider discontinuation of study treatment Assess ECG and monitor lymphocyte counts
Potent inducers of CYP2C9 (Table 21-2)	Stop taking. If not possible, consider discontinuation of study treatment

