1.1.3 Pharmacology of Sphingosine-1-Phosphate (S1P) Receptors

BAF312 (siponimod) acts as a selective modulator of two of the five sphingosine-1-phosphate (S1P) receptors: S1P₁ and S1P₅. T cells selectively require S1P₁ activation for emigration from the thymus, and both T- and B cells require this receptor for egress from peripheral lymphoid organs (Matloubian et al 2004, Brinkmann et al 2004).

Commercially Confidential Information

Two open label trials with another S1P-receptor modulator, fingolimod ([Fu et al 2014a](#), [Fu et al 2014b](#)), suggest an impact on edema formation and improved neurological outcome in ICH and ischemic stroke. However, limitations of the Fu et al. studies include lack of randomization, lack of placebo controls, and small sample sizes.

BAF312 is a second generation S1P receptor modulator that reduces peripheral lymphocyte counts approximately 4 – 6 hours (h) after the first dose. The half-life of BAF312 is approximately 30 h, which allows reversal of pharmacodynamic effects and recovery of the baseline lymphocyte counts within a week after treatment withdrawal. BAF312's mode of action is believed to include S1P₁-mediated prevention of effector lymphocyte recirculation from lymphatic tissue to sites of inflammation, such as the central nervous system (CNS). In addition, there may be direct beneficial effects in the CNS mediated by S1P₁ and/or S1P₅. Evidence from preclinical models suggests that BAF312 may target S1P₁ on astrocytes and/or S1P₅ on oligodendrocytes ([Choi et al 2011](#)).

We seek to evaluate whether reducing peripheral leukocyte count acutely after ICH would reduce PHE and decrease secondary injury after ICH, thereby improving outcomes in a prospective, randomized study with another S1P-receptor modulator, BAF312.

For more details, please see the Investigator's Brochure.

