5.3 Dietary restrictions

- No grapefruit or grapefruit juice is to be consumed during the study until 7 days following the last dose (i.e., Day 21 after ICH).

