6.5 Treating the subject

Once a patient meets all eligibility criteria and is randomized to a treatment arm, the treatment should start as soon as possible, CCI after the time of the ICH, defined as the time the patient was last witnessed to be healthy.

The total treatment lasts 14 days: 7 days of BAF312 with i.v. up-titration CCI (see [Figure 3-1](#)) followed by 7 days of CCI BAF312 p.o. once daily.

Commercially Confidential Information

As described in the accompanying Pharmacy Manual, syringe pump changes must occur every 6 hours, with a window of -15/+30 minutes.

During the i.v. up-titration period patients must be closely monitored. Special attention should be given to monitoring the HR and cardiac rhythm, with continuous CV telemetry in the Stroke Unit/Neurointensive Care Unit (Stroke/NICU) setting for at least the first 48 hours of the i.v. treatment phase. In case of symptomatic bradycardia or cardiac rhythm abnormalities (e.g. atrioventricular blocks or sinus pauses), the Investigator should follow the guidance given in

Section 6.6. Under those predefined conditions a dose may be postponed or skipped, but not more than 2 times in a row.

During the 7 days of i.v. infusion treatment, all patients must undergo a swallowing safety evaluation. Those ICH patients who do not successfully pass a swallowing safety evaluation per the treating hospital's institutional guidelines and practices will not be transitioned to the p.o. phase of treatment, and BAF312 must be discontinued after Day 7. Failure to pass a swallowing safety evaluation should be recorded in the source documentation, and patients who are unable to safely swallow oral medications should continue to be followed for the remainder of the [Assessment schedule](#); they should **not** be terminated from the study. The p.o. phase of treatment consists of five tablets to be taken whole, with or without food, in the morning.

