6.11 Concomitant treatment

Per U.S. and European stroke care guidelines, corticosteroids should not be used for treatment of ICH because they are ineffective and increase complications ([Hemphill et al 2015](#), [Steiner et al 2014](#)).

The Investigator must instruct the patient to notify the study site about any new medications he/she takes after the patient was enrolled into the study.

All prescription medications, over-the-counter drugs and significant non-drug therapies (including physical therapy and blood transfusions) administered or taken within the timeframe defined in the entry criteria prior to the start of the study and during the study, must be recorded on the Concomitant Medications/Significant Non-Drug Therapies CRF.

Medication entries should be specific to trade name, the single dose and unit, the frequency and route of administration, the start and discontinuation date and the reason for therapy.

Each concomitant drug must be individually assessed against all exclusion criteria/prohibited medication. If in doubt, the Investigator should contact Novartis before randomizing a patient or, if the patient is already enrolled, to determine if the patient should continue participation in the study.

7 Study completion and discontinuation

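### The ban on immunosuppressive and chemotherapeutic drugs ends with the last BAF312 dose, but the lymphocyte effect it guards against can last about a week longer

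*Protocol*

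**What the plan says.** Protocol Section 5.2 introduces Table 5-1 by saying that the listed drugs are not "allowed during treatment with BAF312 due to increased risk of immunosuppression, confounding of efficacy and/or potential interaction with study treatment". The first row covers immunosuppressive and chemotherapeutic medications or procedures. The action is to stop the drug or, failing that, to consider stopping study treatment. No period after the last dose is given.

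Three other parts of the protocol bear on how long the reason for the ban lasts:

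- Section 3.7 describes the core effect of BAF312 as "dose-dependent reduction of peripheral lymphocyte counts to 20-30 % of baseline due to their sequestration in the lymphoid tissues". It adds that although the "risk of infection is considered small given the short treatment duration of 14 days, in this critically-ill population this risk might be higher".
- Section 1.1.3 states: "The half-life of BAF312 is approximately 30 h, which allows reversal of pharmacodynamic effects and recovery of the baseline lymphocyte counts within a week" of withdrawal.
- Section 5.3 continues the grapefruit restriction for a week past the last dose and dates its end as Day 21.

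Dosing does not end on the same day for everyone. Under Section 6.5, patients who fail the swallowing evaluation "will not be transitioned to the p.o. phase of treatment, and BAF312 must be discontinued after Day 7". They stay in the study, and Table 8-1 still schedules their Day 14 CT.

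Two other rules touch on these drugs. Exclusion 12 looks back from entry, for example "Moderate immunosuppressives (e.g. azathioprine, methotrexate) and/or fingolimod within 2 months prior to randomization". Section 6.11 looks forward: "Each concomitant drug must be individually assessed against all exclusion criteria/prohibited medication". Neither sets a period counted from the last dose.

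**The concern.** A restriction should last as long as the reason given for it. The leading reason in Section 5.2 is added immunosuppression. That reason does not stop with the last tablet or infusion, because lymphocytes may still be low for some days.

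As written, a site could start methotrexate, cyclosporine or an immunomodulatory antibody the day after the last dose without breaching Section 5.2. In the oral phase or later, the patient may already be at home or in rehabilitation, and lymphocyte counts are largely withheld from sites to protect the blind (Section 8.6.3.1). The person prescribing may therefore not know that the count is low.

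What is at stake is an avoidable overlap of two immunosuppressive effects in patients whom Section 3.7 itself describes as possibly at higher risk of infection.

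**Working it through.** **Inputs from the protocol.** Half-life about 30 h and recovery within a week (1.1.3); lymphocytes at 20-30% of baseline (3.7); last planned dose Day 14, or Day 7 after a failed swallowing evaluation (6.5); CT on Day 14 ± 1 (Table 8-1); about 33 patients per arm (Section 4); CV 90%, 30 evaluable per arm, 40% reduction, one-sided 0.05, 80% power (11.7). From the SAP: at least 2 full i.v. days to enter the per-protocol set (4.1).

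**1. The plan's own recovery figure.** Fraction of drug left = 2^(-t/30), with t in hours.

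- 24 h: 0.574
- 72 h: 0.189
- 168 h (7 days, 168/30 = 5.6 half-lives): 0.021

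This fits recovery within a week. It measures residual drug, not lymphocyte count and not infection risk. The grapefruit date also reproduces for a completer: Day 14 + 7 = Day 21.

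**2. The uncovered week.**

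- Completer, last dose Day 14: Days 15-21.
- Stopped after Day 7: Days 8-14.

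Seven days is an upper limit, since the protocol says within a week.

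**3. How many patients.** The documents give no rate of starting such drugs. Assuming 1-5% of 33 BAF312 patients: 33 × 0.01 = 0.33 to 33 × 0.05 = 1.65.

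**4. Does it reach the primary endpoint?** For completers the uncovered week falls after the CT, apart from at most one day if the scan is on Day 15. Only early stoppers matter.

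- Days from last dose to CT: 13 - 7 to 15 - 7 = 6-8 after a Day 7 stop; 13 - 2 to 15 - 2 = 11-13 after a Day 2 stop.
- Patients, assuming 10-40% stop early and 1-5% of those start such a drug: 33 × 0.10 × 0.01 = 0.033 to 33 × 0.40 × 0.05 = 0.66 on BAF312.
- Log-scale SD at CV 90%: sqrt(ln(1 + 0.81)) = 0.770. With a 40% reduction, -ln(0.6) = 0.511, and 30 per arm, a one-sided t-test has 81.4% power, close to the stated 80%, so this SD agrees with the plan.
- Standard error of the log ratio, unadjusted: 0.770 × sqrt(2/30) = 0.199.
- One affected patient of 30, assuming aPHE is lowered by 20-50%: ln(0.8)/30 = -0.0074 to ln(0.5)/30 = -0.0231. The ratio moves by 0.7-2.3%, or 0.04-0.12 standard errors.
- Expected shift if only the BAF312 arm is affected: 0.033 × 0.0074/0.199 = 0.001 to 0.66 × 0.0231/0.199 = 0.08 standard errors. With similar use and effect in both arms it is about zero.

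**5. What a 7-day extension covers.** After a Day 7 stop it runs to Day 14, so it reaches the CT unless the scan is on Day 15. After a Day 2 stop it runs to Day 9 and leaves 13 - 9 to 15 - 9 = 4-6 days before the scan.

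**The case against.** The strongest reply is that the protocol foresees some overlap. Table 5-1 lets a site end BAF312 when an immunosuppressive cannot be stopped, and Section 7.2 makes prohibited treatment a ground for discontinuation. Few clinicians would start such a drug days after an intracerebral hemorrhage unless it was needed, and any sensible rule would allow needed use. This stands as an argument that the gap is small. It does not close the gap: the fallback deals with a drug in use during dosing and says nothing about a new start afterwards.

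A second reply is that other text already helps, and some of it does:

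- Section 5 opens by asking that patients be reminded of its restrictions throughout the study.
- Section 6.11 requires each new drug to be checked and the sponsor to be asked in case of doubt; the first bullet of exclusion 12, on immunosuppressives, carries no date.
- Section 7.2 keeps collecting concomitant treatments and adverse events after discontinuation.

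These make it likely that such a drug would be noticed. None of them sets a post-dose bar, and the general opening of Section 5 does not override the specific time limit in 5.2.

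Third, no harm has been shown. That is correct: the week is an upper bound, residual drug is not risk, and Section 3.7 calls the infection risk small.

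**Conclusion.** The point holds as a cheap safety improvement. The stated ban ends before its own stated reason does, by up to about 7 days per patient. On an assumed 1-5% start rate, this concerns 0.3-1.7 of 33 BAF312 patients.

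A reader might infer more than the documents support:

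- **That the primary result is at risk.** The expected shift is at most about 0.08 standard errors, even on assumed rates with all affected patients in one arm. The SAP adds a full-analysis-set sensitivity analysis (5.1.1) and a blinded review of set membership (4.1). Handling of discontinuations and supportive analyses is redacted and cannot be judged.
- **That SAP Table 4-1 is defective** because it leaves open the period in which prohibited medication leads to exclusion. Defining it is an optional clarification with a trade-off: running it to the Day 14 CT would drop patients from the primary set for events after they stopped study drug.
- **That more lymphocyte testing is needed.** Extra counts would partly duplicate the scheduled central counts and add chances of unblinding.
- **That every row of Table 5-1 needs a tail.** For strong CYP2C9/3A4 inhibitors, the contrast with the grapefruit rule is an inconsistency without shown harm. Nothing calls for a change to the AV-conduction or inducer rows.

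**What to change.** In Section 5.2 and Table 5-1, extend only the immunosuppressive/chemotherapeutic row until 7 days after the patient's actual last dose. Counting from the actual last dose rather than a fixed study day makes the rule work for early stoppers. Apply it to both arms, since sites are blinded. State that clinically necessary use is allowed, and record any use as Section 6.11 already requires.

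The 4-6 days left open before the CT after a Day 2 stop can be accepted, because the purpose is safety and the lymphocyte rationale ends at about 7 days.

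The cost is one sentence, which under Section 13.1 needs a written amendment and could go in with the next one, plus a site notice. Sample size, power, alpha and the visit schedule do not change. The downside is slightly less freedom in concomitant treatment for about a week after dosing. Antifungals and antibiotics on the inhibitor list are unaffected.
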